- In case a subject was unable to provide consent at the time of enrollment due to the severity of their condition (in accordance with the provisions in 21 CFR 50.24), once the subject is able to understand the nature of the study and the consenting process or the subject's relative becomes available, the subject or relative will be informed that the subject has been enrolled in a clinical study and has been treated on an emergency basis with either standard of care (SOC) or with SOC plus an investigational drug. If the subject or relative refuses consent, the Investigator will stop study assessments and procedures at that time, withdraw the subject from the study, and will not perform any subsequent study assessments.

Study Phases

The study will include the following phases: Screening/Baseline, Treatment Phase, and Discharge.

Planned number of subjects:	An estimated total of 100 subjects will be enrolled in the study (approximately 50 per group).
Diagnosis and main criteria for inclusion:	 Male or non-pregnant female subjects, aged 18 years or older, will be eligible for entry into this study if they are diagnosed with PDIT, as evidenced by all the following at Screening: Core body temperature obtained rectally
	 of >39.5° C (103.1° F). LODS score ≥ 6. In the event of any delay in obtaining the lab results for baseline LODS score determination, subject may be enrolled and randomized if all the other eligibility criteria are met; after enrollment if the pending baseline LODS score turns out to be < 6, subject will be withdrawn from the study and

	subsequently replaced with a new subject
	 Known or suspected recent use of a psychostimulant drug, in the judgement of the investigator.
	• Negative pregnancy test for female subjects. If positive, female subjects must be excluded from participating in the study. In the event of any delay in obtaining pregnancy result, subject may be enrolled and randomized if all other eligibility criteria are met. However, female subjects randomized to Treatment Group A (Ryanodex as adjuvant treatment to SOC) must not be dosed with Ryanodex until a negative result of the pregnancy test is available. If a positive pregnancy test is noted after randomization, subject will be withdrawn from the study and subsequently replaced with a new subject to complete the ITT population.

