A planned sample size of 100 (50 per treatment group) fully eligible (for efficacy) subjects are planned to be randomized in this study.

Baseline:

Baseline body temperature will be the first rectal temperature $>39.5^{\circ}$ C (103.1° F) taken during the Screening Phase. Baseline results for other study assessments will be the value closest in time to the baseline rectal temperature and prior to randomization. The SAP may specify additional data handling rules.

Analysis populations:

The Intent-to-Treat (ITT) population is defined as all randomized subjects whose screening test results for presence of a psychostimulant drug was confirmed by blood test. The ITT population will be used as the primary efficacy population.

The Modified Intent-to-Treat (MITT) population is a subset of the ITT population excluding the subjects who are intubated or with mechanical ventilation or CPAP.

The Per Protocol population (PP) is defined as all ITT subjects who met all inclusion/exclusion criteria, have a baseline and at least 1 post-baseline LODS score, and have no major protocol deviations that could affect the efficacy assessments.

The Safety population is defined as all randomized subjects who received any study treatment (SOC only or SOC with Ryanodex[®]). The Safety population will be used to analyze all safety endpoints using actual treatment received.

Efficacy Analysis: The primary analyses of the primary and secondary efficacy endpoints will be conducted on the ITT population. The MITT and PP population analyses of primary and secondary endpoints will be considered supportive.

Safety Population will be used for the safety analysis. No modeling or inferential statistics will be conducted on the safety assessments.

Eagle Pharmaceuticals, Inc. Protocol EGL-4104-C-1702 Amendment 1

Table 1: Schedule of Assessments

Abbreviations: CCM = continuous cardiac monitoring; ETCO₂ = end-tidal carbon dioxide; ECG = electrocardiogram; med = medication; min = minutes; PT = prothrombin time

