## 8.2 Description of Study Endpoints

### 8.2.1 Efficacy Endpoints

## 8.2.1.1 Primary Efficacy Endpoint

Primary endpoint: Proportion of subjects achieving a total LODS score  $\leq 5$  at or prior to 60 minutes post-randomization.

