## 8.3 Sample Size Determination and Rationale

A total of 100 (50 per treatment group) fully eligible (for efficacy) subjects are planned to be randomized in this study. If the study is used for this sample size calculation. The sample size calculation is based on the assumption that for of subjects who receive SOC therapy and Ryanodex® will achieve a LODS score  $\leq 5$  at or prior to 60 minutes post-randomization, compared with only for of subjects who receive SOC therapy alone. Under the above assumption, subjects per treatment group will be required to meet the Type I error rate of 0.05, 2-sided and more than 90% power; for a total of the subjects for the study.

Sample size estimation is depicted in Figure 2.

Figure 2: Sample Size Yielding More than 90% Power for the Study

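### On the readable text, the ITT (primary) population does not exclude subjects withdrawn and replaced for a baseline LODS below 6; the blanked 8.8.1 may already resolve this

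*Protocol*

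**What the plan says.** **Entry and replacement.** The inclusion criteria in the protocol synopsis require a baseline LODS of at least 6. If laboratory results are late, the subject may be randomised on the remaining criteria, but "after enrollment if the pending baseline LODS score turns out to be < 6, subject will be withdrawn from the study" and a new subject takes the place.

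**Primary population.** Under Analysis populations, the synopsis defines ITT as "all randomized subjects whose screening test results for presence of a psychostimulant drug was confirmed by blood test" and states: "The ITT population will be used as the primary efficacy population". This definition has no condition on LODS, eligibility or withdrawal.

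**Supportive populations.** The Per Protocol set starts from "all ITT subjects who met all inclusion/exclusion criteria", so it does remove these subjects. However, "The MITT and PP population analyses of primary and secondary endpoints will be considered supportive".

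**Sample size.** SAP 8.3 counts 100 subjects, 50 per group, and describes them this way: "fully eligible (for efficacy) subjects are planned to be randomized in this study". The synopsis has the same description.

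**Parallel rule.** In the pregnancy criterion of the synopsis, a subject found ineligible after randomisation is "subsequently replaced with a new subject to complete the ITT population". The LODS criterion also replaces the subject but does not mention ITT.

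**Endpoint.** SAP 8.2.1.1 defines success as a total LODS of 5 or less "at or prior to 60 minutes post-randomization".

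**Not readable.** The ITT definition in SAP 8.8.1, the assumed response rates and required group size in 8.3, and the name of the primary test in 8.11.4.1 are blanked. SAP 8.10 leaves missing-data methods to a separate document.

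**The concern.** The score that triggers withdrawal (below 6) is the same score that defines success (5 or less), provided LODS takes whole-number values. A subject withdrawn under this rule has no room to respond on the primary endpoint. The replacement rule and the fully eligible sample size both suggest that the subject should not count. The ITT sentence as readable keeps the subject if the blood test is positive.

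Two things are at stake. First, two analysts following the readable text could put different people in the primary denominator. Second, subjects whose coded outcome cannot depend on treatment pull the observed difference toward zero, and replacing them does not undo that if they also stay in.

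**Working it through.** **Reproducing the plan's figure.** SAP 8.3 states 50 per group with more than 90% power at two-sided 0.05. This cannot be reproduced because both response rates and the required group size are blanked. All figures below are illustrations.

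**Inputs.**
- From the documents: 50 eligible per arm, 1:1 allocation, two-sided 0.05, replacement of withdrawn subjects.
- Assumed: control rates pB of 20, 30 and 40%; Group A rates pA chosen so that 50 per arm gives 90% power (50.4, 61.7 and 71.6%); a share f of 5 or 10% of the analysed ITT set made up of these subjects, the same in each arm; an unadjusted test.

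**Effect on the difference.** Coded uniformly as responders, each arm's rate becomes f + (1−f)p. Coded uniformly as non-responders, it becomes (1−f)p. In both cases the difference is (1−f)(pA − pB). With 61.7% against 30%, the difference of 31.7 points becomes 0.95 × 31.7 = 30.1 at f = 5% and 0.90 × 31.7 = 28.5 at f = 10%.

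**Effect on power.** With replacement, n per arm = 50/(1−f), which is 52.6 at f = 5% and 55.6 at f = 10%. Power comes from the pooled-variance two-proportion formula, where a and b are the arm rates after coding and m is their mean:

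Φ{ [ |a−b|√n − 1.96√(2m(1−m)) ] / √(a(1−a) + b(1−b)) }

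Example at f = 10%, responder coding, 61.7% against 30%: a = 0.10 + 0.90 × 0.617 = 0.655; b = 0.10 + 0.90 × 0.30 = 0.370; m = 0.513. The bracket is 0.285 × 7.454 − 1.96 × 0.707 = 2.127 − 1.385 = 0.741 (from unrounded values). The denominator is √(0.226 + 0.233) = 0.677. Power is Φ(1.094) = 0.863.

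| Control v Group A | Without them | f = 5%, responder / non-responder | f = 10%, responder / non-responder |
|---|---|---|---|
| 20% v 50.4% | 0.901 | 0.872 / 0.893 | 0.842 / 0.883 |
| 30% v 61.7% | 0.901 | 0.882 / 0.887 | 0.863 / 0.874 |
| 40% v 71.6% | 0.901 | 0.888 / 0.881 | 0.875 / 0.861 |

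The loss at f = 5% runs from 0.901 − 0.893 = 0.008 to 0.901 − 0.872 = 0.029, about 1 to 3 points. At f = 10% it runs from 0.018 to 0.059, about 2 to 6 points.

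**Sensitivity to the assumptions.**
- These ranges are not bounds. With a 10% control rate against 37.0%, responder coding gives about 85% power at f = 5%.
- If 90% power needs only 40 per arm (assumed slack), 50 per arm gives about 0.95 without these subjects, 0.935 to 0.947 at f = 5% and 0.915 to 0.940 at f = 10%.
- If these subjects are dropped as missing, or excluded and replaced, the 50 eligible per arm remain and power does not change.

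**The case against.** The strongest reply is that the governing text cannot be seen. SAP 8.8.1 may carry a LODS condition, in which case only a shortened synopsis sentence needs aligning. That stands, and it limits the point to the readable wording. The synopsis sentence does read as complete, though, so the two places should be checked against each other.

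The surrounding text also points toward exclusion: these subjects are withdrawn and replaced, the pregnancy rule speaks of completing ITT, and the sample size counts fully eligible subjects. This is good evidence of intent, but none of it is an exclusion rule, and the ITT phrase is missing from the LODS criterion.

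Harm needs several conditions at once: late laboratory results, a score below 6, a positive blood test, a silent 8.8.1, and coding as an outcome rather than as missing. SAP 8.9 plans baseline values as covariates, so adjustment for baseline LODS could reduce the loss. This stands too and keeps the size modest.

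Keeping every randomised subject is a respectable principle, and the supportive Per Protocol analysis already removes these subjects. But this ITT set is already conditioned on a blood test, and Per Protocol also removes subjects for other reasons, so it does not isolate the question.

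A reader might also infer that SAP 8.4, which randomises subjects who meet all criteria, contradicts the pending-result allowance. It need not: the allowance is written into the LODS criterion itself, so a subject randomised under it can be read as meeting the criteria. No change to 8.4 is needed.

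**Conclusion.** The point holds as a minor inconsistency in the readable text. The primary population, as defined in the synopsis, does not exclude blood-confirmed subjects whom the plan itself withdraws and replaces for a baseline LODS below 6. If they are kept and coded uniformly, the expected difference shrinks by the factor (1−f). Under the stated assumptions the loss of power is about 1 to 3 points at f = 5% and 2 to 6 points at f = 10%. The share f, the response rates, the coding and the unadjusted test are all assumed.

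Three stronger readings are not supported:
- **That these subjects are automatic successes.** Success needs a score within 60 minutes after randomisation. Withdrawal may leave none, and no coding rule is readable.
- **That the trial is biased toward Ryanodex.** With uniform coding the expected effect is toward no difference, and the documents give no basis for claiming a higher false-positive risk.
- **That the full plan certainly includes them.** The blanked 8.8.1 prevents that conclusion.

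Confidence is medium because of the blanked text.

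**What to change.** Amend the ITT definition in the synopsis, and in SAP 8.8.1 if it does not already say so, to exclude in both arms randomised subjects whose baseline LODS is below 6. Derive that score from values recorded before randomisation, without access to the treatment code. Report the number excluded by arm. Analyse the primary endpoint in all randomised subjects with blood-confirmed drug use as a sensitivity analysis, and state in advance how the withdrawn subjects are coded.

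The cost is wording in one or two places and one extra analysis, with no enrolment beyond the replacement already planned. The downside is a small post-randomisation departure from all-randomised ITT in an open-label trial. Deriving the score without the treatment code reduces that risk but does not remove it, which is why the counts by arm and the sensitivity analysis belong with the change.

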The Logistic Organ Dysfunction System (LODS) provides an objective tool for assessing organ dysfunction in critical patients. The LODS identifies organ dysfunction for 6 organ systems: neurologic, cardiovascular, renal, pulmonary, hematologic and hepatic, taking into account both the relative severity among organ systems and the level of severity within an organ system.

Standard of Care

Implementation of standard of care (SOC) should be initiated as quickly as possible after admission of the subject to the PHEC. For the purpose of this study, SOC is defined as efficient body cooling by physical methods and supportive measures, implemented as following:

Body Cooling

- *Ice packs*: should be placed to neck, axilla, and inguinal regions.
- **Evaporative cooling**: application of water (room temperature) over the body surface, via mist application with continuous use of a fan. Subjects may be covered with a thin sheet. Do not use ice/cold water immersion because of concerns with shivering (which could potentially worsen hyperthermia), and the need for IV access and other monitoring measures and medical procedures.
- **Benzodiazepines**: may be administered to ameliorate shivering induced by cooling methods, as deemed necessary by the Investigator.

Supportive Measures

Randomized subjects will also receive any other medical treatments and/or supportive measures (IV fluids, respiratory support) for the adequate treatment of existing complications or comorbidities (e.g. dehydration, seizures, aggressiveness, asthma) following acceptable medical practice, and as deemed necessary by the Investigator.

Treatment Groups

Upon admission to the PHEC, eligible patients with PDIT will be randomized in a ratio to one of the following treatment groups:

- Group A: Ryanodex[®], as added treatment to SOC
- Group B: SOC only

The Investigator will make all reasonable efforts to perform the **second** drug screen test during the screening process or as soon as feasible after randomization. The **second** drug screen test may not be feasible in some subjects, due to the dehydration, use of oxygen therapy and/or endotracheal intubation commonly seen in patients with PDIT, which may result in dryness of the oral mucosa. A blood sample for testing for the presence of psychostimulant drugs will also be collected after randomization.

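### The primary ITT set admits only randomised subjects with a blood-confirmed drug result, so untested subjects leave it along with true negatives, on tests that can fall after allocation is known

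*Protocol*

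**What the plan says.** The protocol synopsis (Analysis populations) defines ITT as "all randomized subjects whose screening test results for presence of a psychostimulant drug was confirmed by blood test" and adds: "The ITT population will be used as the primary efficacy population". SAP Section 8.11.4.1 also places the primary analysis on ITT. The two other efficacy sets are nested in it: the MITT "population is a subset of the ITT population excluding the subjects who are intubated or with mechanical ventilation or CPAP", and the PP set "is defined as all ITT subjects who met all inclusion/exclusion criteria". Only the Safety set does not depend on drug confirmation.

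Entry does not require a positive test. The synopsis inclusion criterion is "Known or suspected recent use of a psychostimulant drug, in the judgement of the investigator".

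On timing, the synopsis (Treatment Groups) asks for the second "drug screen test during the screening process or as soon as feasible after randomization", and says: "A blood sample for testing for the presence of psychostimulant drugs will also be collected after randomization". It also warns that the second "drug screen test may not be feasible in some subjects, due to the dehydration, use of oxygen therapy and/or endotracheal intubation". SAP Section 8.5 states that the study is open-label.

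Two further synopsis provisions matter. Subjects found after randomisation to have a baseline LODS below 6 or a positive pregnancy test are withdrawn and replaced. A subject enrolled without consent who later refuses, or whose relative refuses, has no further study assessments.

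SAP Section 8.8.1 (ITT) breaks off before its definition, and Section 8.11.5 (Supportive Analysis) is empty. Section 8.10 leaves missing-data methods to a separate SAP.

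**The concern.** An ITT label tells readers that the groups are compared as randomised. This set is instead selected on a test result, and its wording treats a subject who tested negative and a subject who was never tested alike: neither has a confirmed result.

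The two cases differ. Drug exposure precedes randomisation, so removing true negatives identified by a complete assay that cannot depend on arm leaves a fair comparison. Whether a test was done is another matter. A screen done before randomisation cannot depend on arm. A screen deferred until afterwards can, and so can the blood draw. The stated reasons for an infeasible screen, such as intubation and oxygen therapy, mark severity and so plausibly relate to a LODS endpoint. Consent refusal is another route to a missing result if blood had not yet been drawn.

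There is also a tension within the definitions. The MITT set is formed by removing intubated subjects from ITT, so the sponsor expects some in ITT; yet intubation is a named reason why the second screen may be missing. This is not a contradiction, since another screening result may exist, but it shows that a rule is needed. At stake are selection bias in the primary comparison and some loss of power.

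**Working it through.** **The plan's own figure.** SAP Section 8.3 gives 100 subjects (50 per arm), two-sided alpha 0.05 and more than 90% power. Both response rates and the required number per group are blanked, so it cannot be reproduced. As a consistency check, a pooled two-proportion test with 50 per arm reaches 90% power for pairs such as 20% v 50%, 30% v 62% or 40% v 72%. The stated size is plausible but not verifiable.

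**Inputs.** From the documents: 50 per arm, 1:1, alpha 0.05 two-sided. Assumed: response rates, loss rates, and a pooled z-test (the planned test is blanked).

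**Step 1: no treatment effect.** Let p be the true response, and qr and qn the shares of responders and non-responders lost. The analysed response rate is

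p(1 - qr) / [p(1 - qr) + (1 - p)(1 - qn)].

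Example, p = 0.40, non-responders only, 20% v 10%: A = 0.40/(0.40 + 0.48) = 45.5%; B = 0.40/(0.40 + 0.54) = 42.6%; false difference +2.9 points. Expected losses are 50 x 0.6 x 0.2 = 6 v 50 x 0.6 x 0.1 = 3 subjects.

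Type I error is summed exactly over all tables of kept counts. Figures are for p = 40%, with the range over 20-50% in brackets.

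| Loss, A v B | Type I error, % | False difference, points |
|---|---|---|
| None | 5.2 (5.0-5.7) | 0 |
| 10% v 10%, unrelated to outcome | 5.1 (5.1-5.1) | 0 |
| 20% v 0%, unrelated to outcome | 5.1 (5.0-5.1) | 0 |
| Non-responders 10% v 5% | 5.3 (5.2-5.3) | +1.3 (0.9 to 1.4) |
| Non-responders 20% v 10%, responders 10% v 5% | 5.4 (5.3-5.4) | +1.6 (1.1 to 1.6) |
| Non-responders only, 20% v 10% | 6.0 (5.7-6.0) | +2.9 (2.1 to 2.9) |
| Responders only, 20% v 10% | 5.9 (5.7-6.0) | -2.7 (-1.7 to -2.9) |

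Heavier loss does more. By normal approximation, with 40% true response and only 10% response among the untested, 20% v 10% untested gives 6.7%, and 30% v 10% gives about 13%. Under no effect, false-positive bias needs loss that relates to outcome and differs by arm.

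**Step 2: true effect, equal loss.** Lose 20% of non-responders in both arms, with true rates of 20% v 50%:

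- control: 0.20/(0.20 + 0.80 x 0.80) = 0.20/0.84 = 23.8%
- treated: 0.50/(0.50 + 0.50 x 0.80) = 0.50/0.90 = 55.6%

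A 30-point difference becomes about 32 points although loss does not differ by arm.

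**Step 3: power under adverse loss.** Control rates 20%, 30% and 40%, with true differences of 30.3, 31.6 and 31.5 points. Exact power without loss is 90-91%. With 20% v 10% of responders lost it is 80-81%. Expected losses in A run from 50 x 0.503 x 0.2 = 5.0 to 50 x 0.715 x 0.2 = 7.2 subjects; in B from 50 x 0.2 x 0.1 = 1.0 to 50 x 0.4 x 0.1 = 2.0.

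**Step 4: cost of keeping untested subjects.** Let m be the share untested and g the share of these who are drug-negative with no treatment effect. The effect d becomes d(1 - mg). Assume that 50 per arm just gives 90% and control response is 20-40% (normal approximation).

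| Rule | Power, % |
|---|---|
| Keep, m = 10%, g = 20% (0.98d) | 88.7-88.9 |
| Keep, m = 20%, g = 20% (0.96d) | 87.2-87.6 |
| Keep, m = 10%, g = 100% (0.90d) | 82-83 |
| Drop 10%, no replacement (45 per arm) | 86.6 |
| Drop 20%, no replacement (40 per arm) | 82.3 |

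Keeping costs less power than dropping without replacement unless about half of the untested (47-57%) are drug-negative.

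**The case against.** The strongest reply is that this is one synopsis sentence, and a rule for untested subjects belongs in exactly the text that cannot be read: Sections 8.8.1 and 8.11.5, and the separate SAP. That stands to this extent: a reader might infer that the plan has no all-randomised efficacy analysis, and the documents do not support that. But the synopsis states a rule rather than leaving a gap, and its readable wording drops untested subjects from the primary set and from both sets nested in it.

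Second, the infeasibility warning concerns the second screen and dryness of the mouth, not the blood draw. The first screen and the exact time of the blood draw are not visible, and blood is taken for other purposes anyway. This stands. A reader might infer that blood results will often be missing, or that loss will favour one arm; no text says either.

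Third, the moderate scenarios do little harm: several type I figures lie within the 5.0-5.7% that discreteness gives without any loss. This also stands and limits the severity. A reader who infers that the primary result is biased goes beyond the documents, from which neither size nor direction can be derived.

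Fourth, a rule to keep every untested subject could collide with the withdrawal and replacement provisions. A subject with baseline LODS below 6 already meets the endpoint of 5 or less, so retaining such subjects would add automatic responders. This is right, and the fix must allow for it.

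**Conclusion.** The concern holds in a limited form and should be fixed. The readable definition makes membership of the primary set conditional on tests that can be done after open-label allocation, and it removes untested subjects together with true negatives. Excluding true negatives is a defensible choice and is not the defect.

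The likely effect on type I error is small for moderate loss (5.3-6.0% against about 5.2%); much larger values need heavy, one-sided loss. The fall in power to 80-81% needs loss confined to responders at twice the rate in Group A. It would be wrong to conclude that equal loss is harmless: under a true effect, outcome-related loss shifts the difference even when it is the same in both arms. All these figures rest on assumed response and loss rates and an assumed test.

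Whether 50 per arm already means drug-confirmed subjects after replacement is unclear. SAP Section 8.3 calls the 100 fully eligible for efficacy, but the visible replacement provisions cover only low baseline LODS and a positive pregnancy test.

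**What to change.** In the protocol synopsis and Section 8.8.1:

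1. On drug-test grounds, exclude from the primary set only subjects with a documented negative blood result. Keep those whose screen or blood test is missing or infeasible. State that this does not override the synopsis provisions for subjects withdrawn and replaced (baseline LODS below 6, positive pregnancy test), and say how subjects who refuse consent are counted.
2. Unless the blanked text already has it, add a sensitivity analysis of the primary endpoint in all randomised subjects as randomised, with those withdrawals shown separately.
3. Report negative and missing drug tests by arm.
4. Optionally, rename the set drug-confirmed rather than ITT. Modified ITT would clash with the existing MITT label.

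The cost is a change of wording, one sensitivity analysis and one table. The statistical downside is slight dilution: about 89% rather than 90% power if 10% are untested and one in five of these is drug-negative. If dropped subjects would otherwise be replaced, dropping keeps 90% and the dilution is a net cost; without replacement, dropping 10% gives 86.6%, so keeping them is the cheaper choice unless about half are drug-negative.

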Subjects in Group A will receive SOC immediately followed by an initial dose of Ryanodex[®] (study drug) of 2.5 mg/kg administered as an IV bolus. Initial dose of Ryanodex[®] should be administered within minutes of randomization. The goal is to achieve an adequate clinical response, which is defined as meeting both of the following criteria:

2. Logistic Organ Dysfunction System (LODS) score ≤ 5

If the subject is not showing adequate clinical response between 10 and 30 minutes after the initial dose, or the subject had achieved an adequate response but afterwards signs/symptoms believed to be associated with PDIT re-appear a

second IV bolus dose of 2.5 mg/kg of Ryanodex[®] may be administered between 10 and 30 minutes following the initial dose. This repeat dosing is permitted, as deemed necessary by the Investigator, unless the subject demonstrates clinically significant signs/symptoms of dantrolene-related adverse reactions.

The Investigator must clearly record all clinical assessments and symptoms leading to repeat dosing of Ryanodex[®]. The total administered dose of Ryanodex[®] in a 24-hour period should not exceed 10 mg/kg.

Individual Subject Stopping Rules

- The Investigator may consider stopping study drug if the subject demonstrates clinically significant signs/symptoms of dantrolene toxicity, which may include, but are not limited to, the following: increased skeletal muscle weakness; worsening in the state of consciousness (e.g., lethargy, coma); worsening respiratory status, including increased respiratory muscle weakness, vomiting, diarrhea, or crystalluria; providing none of these signs/symptoms are not attributable to PDIT, a comorbid condition (e.g., asthma, epilepsy, pneumonia) or a concomitant medication (e.g., sedatives).
- The Investigator may stop study drug at any time for that subject's well-being if the Investigator believes that the subject has experienced a serious AE (SAE) possibly related to study drug or a clinically significant non-serious AE possibly related to study drug.
- The subject will be withdrawn from the study if a diagnosis had been made for which dantrolene is the SOC (e.g., malignant hyperthermia [MH]), and treatment with commercially available dantrolene should be initiated.

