# 8.0 STATISTICAL CONSIDERATIONS

This section presents general information about statistical considerations and concepts such as randomization, covariates, statistical power, sample size, and a brief discussion on analysis methodology, as well as some data conventions. Detailed descriptions of the statistical analysis methods and data conventions will be included in a separate document; i.e., the Statistical Analysis Plan (SAP).

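### Does the MITT exclusion of ventilated subjects, which shows no time point, bias the supportive efficacy analysis?

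*Protocol*

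**What the plan says.** The synopsis, under Analysis populations, defines MITT as a subset of ITT, "excluding the subjects who are intubated or with mechanical ventilation or CPAP". No time point is visible. ITT is the primary efficacy population, and "The MITT and PP population analyses of primary and secondary endpoints will be considered supportive".

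SAP Section 8.8.2 carries the MITT heading, but its definition is blank after the verb; only the statement that the analysis is supportive can be read. Section 8.11.5 (Supportive Analysis) is a heading without text. Detail is deferred: Section 8.0 says "Detailed descriptions of the statistical analysis methods and data conventions will be included in a separate document", and the synopsis, under Baseline, adds "The SAP may specify additional data handling rules".

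Four other statements bear on the point:
- Under Standard of Care, the synopsis allows randomised subjects in either group to receive respiratory support when the investigator judges it necessary.
- Under Treatment Groups, when discussing whether a drug screen near entry is feasible, it mentions "use of oxygen therapy and/or endotracheal intubation commonly seen in patients with PDIT".
- Under Individual Subject Stopping Rules, possible signs of drug toxicity include "worsening respiratory status, including increased respiratory muscle weakness".
- On the endpoint scale, "The LODS identifies organ dysfunction for 6 organ systems: neurologic, cardiovascular, renal, pulmonary, hematologic and hepatic".

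**The concern.** Without a time point the exclusion has two readings. Under the first, it removes subjects already ventilated at entry. Under the second, it also removes subjects first ventilated after randomisation.

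The second reading would matter. The trial is open label (SAP Section 8.5), respiratory support is discretionary, the drug is listed as possibly affecting respiratory muscles, and pulmonary function contributes to the LODS total on which the primary endpoint rests. Dropping subjects for later ventilation would then select on something related to both arm and outcome. MITT could differ from ITT for that reason alone, and a reader might take the difference as information about the treatment effect. The direction cannot be known in advance: the drug could raise or lower the need for ventilation.

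**Working it through.** **Inputs from the documents.** 50 subjects per group (SAP Section 8.3), 1:1 allocation (Section 8.4), endpoint LODS total of 5 or less by 60 minutes after randomisation (Section 8.2.1.1). The response rates in Section 8.3 are not readable, so the planned power cannot be reproduced, and no ventilation rates are given. Every rate below is an assumption.

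**Reading 1, status at entry.** Let *p* be the response rate in the whole arm, *w* the share excluded and *r* the response rate among those excluded. The MITT response rate is (p − w·r)/(1 − w). Randomisation makes *w* and *r* equal between arms in expectation. With no true effect, p = 0.40, w = 0.15 and r = 0.05, each arm gives (0.40 − 0.0075)/0.85 = 0.462. The expected bias is zero.

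**Reading 2, later ventilation included.** Let *v* be the share of non-responders and *u* the share of responders ventilated after randomisation. The MITT response rate is p(1 − u)/[p(1 − u) + (1 − p)(1 − v)]. Take p = 0.40 in both arms (no true effect) and u = 0.

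| Non-responders ventilated, A v B | Share of arm, A v B | MITT rate A | MITT rate B | Difference | SE | Difference/SE |
|---|---|---|---|---|---|---|
| 15% v 5% | 9% v 3% | 0.40/0.91 = 44.0% | 0.40/0.97 = 41.2% | +2.7 points | 10.2 | 0.27 |
| 30% v 10% | 18% v 6% | 0.40/0.82 = 48.8% | 0.40/0.94 = 42.6% | +6.2 points | 10.6 | 0.59 |

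The SE is √[a(1 − a)/n_A + b(1 − b)/n_B], where *a* and *b* are the two MITT rates. The remaining numbers are 45.5 and 48.5 in the first row, and 41 and 47 in the second.

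**Sensitivity.**
- Over response rates of 20% to 60%, the two scenarios give 1.9 to 2.8 and 4.6 to 6.3 points.
- If responders are ventilated at one third of the non-responder rate, they give 1.9 and 4.4 points.
- If ventilation is unrelated to response (u = v), or equally frequent in both arms, the bias is zero. If the arms swap rates, the sign reverses.
- Larger imbalances, using the first formula with r = 0.05: 20% of A and 10% of B ventilated gives 0.39/0.80 − 0.395/0.90 = +4.9 points; 30% v 10% gives 0.385/0.70 − 0.395/0.90 = +11.1 points.

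**Is the time point really absent from the plan?** The synopsis drops words without any mark. Under Treatment Groups the allocation ratio has lost its numbers, although SAP Section 8.4 gives 1:1. The interval from randomisation to the initial dose has lost its number of minutes. The list of response criteria starts at item 2. A short timing phrase could have gone from the MITT sentence in the same way. The ITT, MITT and PP definitions in Sections 8.8.1 to 8.8.3 are all blank, and the separate SAP is not among the documents.

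**The case for a change.** The case for acting is respectable. The MITT sentence reads grammatically as it stands. The same part of the synopsis does give time anchors elsewhere: baseline values must precede randomisation, and PP requires a LODS score after baseline. Ventilation after randomisation is foreseeable, because respiratory support is expressly allowed. Two programmers could build different populations from the visible words, and in an open-label trial the rule should be fixed before anyone looks at the data. The remedy would be one phrase.

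Most of this stands as description. The visible sentence is ambiguous, and the bias follows under the second reading. What does not stand is the step from there to a defect in the plan. A sentence that reads smoothly does not show that nothing was removed, and the places where the rule would normally be written in full cannot be read. The visible wording describes a current state and does not refer to ventilation at any time during the study; the nearest mention of intubation concerns testing close to entry. That leans towards entry status, although no readable sentence confirms it. Nothing in the documents says that ventilation would differ by arm: respiratory support is available to both, and respiratory weakness is one item in a list of possible signs.

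**Conclusion.** No change to the plan follows. On the natural reading, the exclusion uses status at entry and the expected bias is zero. On the other reading, the bias is real but cannot be estimated from the documents. The figures of 2.7 to 11.1 points rest on assumed response and ventilation rates, on a two- to threefold imbalance between arms, and on few or no responders among the ventilated. In the two tabulated scenarios the bias is 0.27 and 0.59 of a standard error.

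The consequence is limited in either case. The primary conclusion rests on ITT, and MITT is declared supportive. ITT and Safety are not reduced by this exclusion. The matter comes down to writing out a time point that Section 8.8.2 or the separate SAP may already contain, and that an analyst building the population would ordinarily take as status at or before randomisation. This conclusion would change only if those unseen texts expressly extended the exclusion to ventilation begun after randomisation.
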